9.7.1.6 Efficacy Analyses

The FAS will be used as the primary analysis set for all efficacy analyses, while the PP will be used as a supportive analysis. Unless specified otherwise, a 2-sided $\alpha=0.05$ significance level will be used for all efficacy analyses.

Primary Efficacy Analysis

The primary efficacy endpoint is the change in BMI from Baseline to Week 52. The change from baseline in BMI will be analyzed using analysis of covariance model (ANCOVA) with factors of treatment, sex (male and female) as fixed effect, and the baseline age and BMI as covariates. The missing values will be imputed using a pattern mixture model utilizing multiple imputation (MI) assuming the missing values are missing not at random (MNAR). The missing values will be imputed at each visit using all available values including the retrieved measurement from the postdiscontinuation data. The details of the analysis model and missing value imputation method will be further described in the SAP.

In addition, the following analyses will also be considered as sensitivity analyses:

- PP analysis: The same primary efficacy analyses described above will be repeated based on the PP.
- Change from baseline in standardized BMI score (Z-score): The same primary efficacy analyses described above will be repeated using Z-score.

Subgroup analyses and additional sensitivity analyses, if appropriate, may also be performed and will be described in the SAP.

Key Secondary Efficacy Analysis

The key secondary efficacy endpoint is the proportion of subjects achieving at least a 5% BMI reduction at Week 52. The secondary efficacy endpoint will be analyzed only if the test for the primary efficacy endpoint is statistically significant.

The proportion of subjects achieving at least a 5% BMI reduction at Week 52 will be analyzed using a logistic regression model with factors of treatment, and sex (male and female), and baseline BMI as a covariate using FAS. Subjects with any missing assessment at Week 52 will be considered as treatment failures in this analysis.

Other Secondary Efficacy Analyses

Unless specified, for all other secondary efficacy endpoints, the continuous variables will be analyzed using mixed effect model repeated measurement analysis (MMRM) and categorical variables will be analyzed using the Cochran Mantel Haenszel test, Chi-square test, or logistic regression as appropriate. Additional analysis may be performed as needed using appropriate statistical methodologies as specified in SAP.

Subgroup analyses will be performed on the primary efficacy endpoint, including sex (male and female), race (white, black, Asian, and other). Additional subgroups may be explored, if deemed necessary.

No adjustment for multiplicity is planned for other secondary endpoints, subgroup, and sensitivity analyses.

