9.7.1.1.2 SECONDARY EFFICACY ENDPOINTS

KEY SECONDARY ENDPOINT

- Proportion (%) of subjects achieving at least a 5% BMI reduction at Week 52

OTHER SECONDARY ENDPOINT

- Proportion (%) of subjects achieving at least a 5% BMI reduction at Week 12
- Proportion (%) of subjects achieving at least a 10% BMI reduction at Week 52
- Percentage change in BMI from Baseline to Week 52
- Association between change and percentage change in BMI from Baseline to Week 52 with the outcome of achieving at least a 5% BMI reduction at Week 12 (revised per Amendment 02)
- Association between the proportion (%) of subjects achieving at least a 5% or 10% BMI reduction at Week 52 with the outcome of achieving at least a 5% BMI reduction at Week 12 (revised per Amendment 02)
- Change in waist circumference from Baseline to Week 52
- Change in HbA_{1c} from Baseline to Week 52
- Change in fasting glucose, fasting insulin, and HOMA-IR from Baseline to Week 52
- Change in BP (systolic and diastolic) and heart rate from Baseline to Week 52
- Change in fasting lipid profile (total cholesterol, LDL cholesterol, HDL cholesterol, triglycerides) from Baseline to Week 52
- Proportion (%) of subjects with prehypertension or primary hypertension at Week 52
- Proportion (%) of subjects with dyslipidemia at Week 52

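### The key secondary logistic model leaves out baseline age, which the primary ANCOVA includes for the same Week 52 BMI data: a minor improvement at almost no cost

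*Protocol*

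**What the plan says.** Section 9.7.1.6 of the Protocol specifies both models.

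- **Primary.** Change in BMI from Baseline to Week 52 is analyzed by ANCOVA "with factors of treatment, sex (male and female) as fixed effect, and the baseline age and BMI as covariates".
- **Key secondary.** The proportion with at least a 5% BMI reduction at Week 52 is analyzed by a "logistic regression model with factors of treatment, and sex (male and female), and baseline BMI as a covariate using FAS". It is tested only if the primary result is significant, and a missing Week 52 assessment counts as treatment failure.

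The Synopsis gives the same two covariate lists. The primary paragraph sends further model detail to the SAP. The key secondary paragraph has no such deferral, so its model stands as written.

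Section 9.5.1.1 collects date of birth or age at the first visit, and section 9.7.1.4 lists age as a baseline variable. Section 9.4.3 makes sex the only stratification factor.

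Section 9.7.2 bases the key secondary power on an unadjusted two-sided Chi-square test: 20% against 40%, 130 per arm, 40% dropout, power greater than 78%.

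**The concern.** The key secondary endpoint is a cut-point applied to the same baseline and Week 52 BMI values that give the primary endpoint. The plan treats age as worth adjusting for when it models the mean change in 12 to 17 year olds. It then drops age when it models the proportion passing 5%, and does not say why.

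If age predicts who reaches a 5% reduction, a logistic test that ignores it has less power than one that includes it. What is at stake is a little efficiency, and consistency between the two analyses that form the only ordered testing sequence in the plan. The validity of the test is not at stake.

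**Working it through.** **1. Reproduce the stated power.** Inputs from section 9.7.2: 130 per arm, 40% dropout, rates 0.20 and 0.40, two-sided α = 0.05. Evaluable per arm: 130 × 0.6 = 78.

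Formula: power = Φ{[Δ − 1.96·√(2p̄(1−p̄)/n)] / √[(p₀(1−p₀) + p₁(1−p₁))/n]}

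- p̄ = 0.30 and Δ = 0.20
- null standard error = √(2 × 0.30 × 0.70 / 78) = 0.0734
- alternative standard error = √((0.16 + 0.24)/78) = 0.0716
- power = Φ[(0.20 − 1.96 × 0.0734)/0.0716] = Φ(0.784) = 78.4%

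This agrees with the stated figure of more than 78%. No covariate enters the calculation, so the promise does not depend on age being in the model.

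**2. Size the gain from adding age.** The documents give no relation between age and response, so a range has to be assumed: an odds ratio of 1.0 to 2.0 per standard deviation (SD) of age. If ages are spread evenly over 12 to 17, the SD is about 1.7 years. An odds ratio of 1.5 per SD is then about 1.5^(1/1.7) = 1.27 per year, and 2.0 per SD is about 2^(1/1.7) = 1.50 per year.

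Simulation model: logit P(response) = a(arm) + ln(OR)·x, with x standardized age, uniform with SD 1. The arm intercepts were solved so that the overall response rates stay at the target values. Sex was generated with no effect. Treatment was tested by a likelihood-ratio test at two-sided 0.05, once adjusted for sex and once for sex and age, on the same simulated data sets. There were 4,000 replicates, giving a Monte Carlo standard error of about 0.7 point per entry. Baseline BMI was left out of both models.

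Two settings were run:

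- **A:** the protocol's own, 78 evaluable per arm, 40% against 20%.
- **B:** all 130 per arm with missing counted as failure. If the 20% and 40% rates describe subjects observed at Week 52, they become 0.6 × 20% = 12% and 0.6 × 40% = 24%.

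| Assumed OR per SD of age | A: without age → with age | Change | B: without age → with age | Change |
|---|---|---|---|---|
| 1.0 | 78.8% → 78.7% | −0.1 | 71.6% → 71.4% | −0.2 |
| 1.2 | 79.7% → 79.6% | −0.1 | 71.4% → 71.8% | +0.4 |
| 1.5 | 78.4% → 80.2% | +1.8 | 72.8% → 73.7% | +0.9 |
| 2.0 | 78.9% → 82.1% | +3.2 | 73.2% → 75.0% | +1.8 |

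The gain runs from about 0 to about 3 points. The small negative entries are within simulation error.

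**The case against.** The best defence is that nothing is broken. The model already contains the stratification factor and baseline BMI. Omitting a further covariate neither biases a randomized comparison nor inflates the type I error. The two endpoints also differ: one is an absolute change, the other a relative threshold with missing values counted as failures. Identical covariates are therefore desirable rather than obligatory. All of this stands, and it is why the point is minor. It does not explain why age was dropped.

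It can also be said that the change is not wholly free. Odds ratios are non-collapsible, so adding a prognostic covariate changes the quantity estimated: the reported odds ratio becomes conditional on age too. That also stands and should be acknowledged. Overfitting is not a serious worry. The planning rates imply about 78 × 0.40 + 78 × 0.20 = 46.8 responders for four model terms, or roughly 12 per term.

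Two stronger readings are tempting, and the Protocol supports neither.

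- A reader might infer that the key secondary falls short of its stated power because age is missing. It does not: the stated figure never used covariates. The lower values in setting B come from counting missing as failure, under the assumption stated there. That is a separate matter, and adding age would not resolve it.
- A reader might infer that the Week 52 hypertension and dyslipidemia proportions are analyzed without regard to baseline status. Section 9.7.1.6 says only that "categorical variables will be analyzed using the Cochran Mantel Haenszel test, Chi-square test, or logistic regression as appropriate". A Cochran-Mantel-Haenszel test can stratify by baseline status and a logistic model can include it. The Protocol fixes no strata or covariates for these endpoints. Such detail commonly sits in the SAP, which was not available for this point. The Protocol also gives no rates from which a power loss could be computed.

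**Conclusion.** The inconsistency is real and is fixed in the Protocol text: baseline age is in the primary model, absent from the key secondary model, and no reason is given. Its consequence is small. Adding age would raise key secondary power by about 0 to 3 points, and by essentially nothing if the odds ratio per SD is 1.2 or less. These figures rest on an assumed age effect, a uniform age distribution, and simulated models without baseline BMI. There is no bias, and the stated power is not undercut. This is a minor improvement at almost no cost.

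**What to change.** In the Synopsis and in section 9.7.1.6, amend the key secondary model to a logistic regression with treatment and sex as factors and baseline age and baseline BMI as covariates, matching the primary analysis. Carry the same wording into the SAP, and make the change before unblinding. If the sponsor prefers to keep the model as it is, one sentence giving the reason would settle the point.

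The cost is a wording change only. No new data, visits or subjects are needed. The report should state that the treatment odds ratio is conditional on sex, age and baseline BMI.

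### Percentage change in BMI at Week 52 is analysed by default under a different missing-data assumption from the primary, although it is the same measurement with the same gaps

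*Protocol*

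**What the plan says.** Protocol Section 9.7.1.6 states: "The primary efficacy endpoint is the change in BMI from Baseline to Week 52". The model is an ANCOVA with treatment and sex as factors and baseline age and baseline BMI as covariates. Missing values are filled by pattern-mixture multiple imputation, "assuming the missing values are missing not at random (MNAR"), at each visit and "using all available values including the retrieved measurement from the postdiscontinuation data". The mechanism is deferred: "The details of the analysis model and missing value imputation method will be further described in the SAP".

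Section 9.7.1.1.2 lists "Percentage change in BMI from Baseline to Week 52" among the other secondary endpoints, and Section 8.2 gives it its own objective of demonstrating efficacy against placebo.

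Its analysis comes from the default later in Section 9.7.1.6. The sentence begins "Unless specified, for all other secondary efficacy endpoints" and continues that "the continuous variables will be analyzed using mixed effect model repeated measurement analysis (MMRM"). The default states no imputation and no missing-data assumption, and does not say how post-discontinuation values are handled. The section adds: "No adjustment for multiplicity is planned for other secondary endpoints, subgroup, and sensitivity analyses".

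For another re-expression of BMI, the standardized Z-score, the same section plans to repeat the primary analysis as a sensitivity analysis. Percentage change gets no such treatment.

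**The concern.** For one subject, percentage change is 100 × (Week 52 BMI − baseline BMI) / baseline BMI. With baseline observed, it is missing exactly when the primary variable is missing. The protocol takes those absent values to be MNAR for one endpoint. For the other it uses a method whose validity, without imputation, rests on MAR. It gives no reason for the difference.

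The revision history suggests a possible explanation. The primary moved from a repeated-measures model to a Week 52 ANCOVA at v5.0, while the MMRM default for secondary endpoints reads the same in the v4.0 text. That is background only; the inconsistency lies within the current section.

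What is at stake is interpretation. The trial plans for 40% dropout, and percentage change has an efficacy objective and is tested at two-sided 0.05 without adjustment. If the absolute and percentage results point to different relative effects or fall on different sides of 0.05, a reader cannot tell how much is due to rescaling and how much to the change of missing-data assumption.

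**Working it through.** **1. The plan's own figure.** Section 9.7.2 gives 130 per arm, 40% dropout, SD 2.2 kg/m², a difference of 1 kg/m², two-sided α = 0.05 and power of at least 80%.

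- Evaluable per arm: 130 × 0.6 = 78.
- Noncentrality: 1 / (2.2 × √(2/78)) = 2.84.
- Power: 80.5% (noncentral t) or 81.0% (normal).

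The stated figure reproduces. These inputs are used below.

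**2. What an MNAR assumption does to the target effect.** Let the effect under MAR be 1 kg/m² in favour of drug. Let m_A and m_P be the fractions of Week 52 BMI missing on drug and placebo. Let d_A and d_P be the amounts by which the MNAR assumption worsens the missing values relative to MAR. Then

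MNAR effect = 1 − m_A·d_A + m_P·d_P.

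The protocol gives no value for any d and no missingness by arm, so each case is an assumption.

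- Jump to placebo (d_A = 1, d_P = 0), equal missingness m: effect = 1 − m, which is 0.9, 0.8 and 0.6 at 10%, 20% and 40%.
- Same delta of 1 in both arms, 40% missing in each: 1 − 0.4 + 0.4 = 1.0.
- Same delta, 30% missing on drug and 50% on placebo: 1 − 0.3 + 0.5 = 1.2.
- Same delta, 50% missing on drug and 30% on placebo: 1 − 0.5 + 0.3 = 0.8.

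**3. Simulation check.** There were 1000 runs with 130 per arm and 10 imputations pooled by Rubin's rules. Each subject had an interim and a Week 52 value, with SD 2.2, assumed correlation 0.7, an assumed interim difference of 0.7 and a Week 52 difference of 1. The interim value was always observed and Week 52 values were removed at random. Imputation under MAR stood in for MMRM, and arms were compared by means without covariates.

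| Assumption for missing values | Missing, drug / placebo | Effect, MNAR | Effect, MAR | Power, MNAR | Power, MAR |
|---|---|---|---|---|---|
| Jump to placebo | 10% / 10% | 0.90 | 1.00 | 92% | 94% |
| Jump to placebo | 20% / 20% | 0.80 | 1.00 | 84% | 93% |
| Jump to placebo | 40% / 40% | 0.60 | 1.01 | 48% | 88% |
| Equal delta of 1 | 40% / 40% | 1.01 | 1.01 | 87% | 88% |
| Equal delta of 1 | 30% / 50% | 1.21 | 1.01 | 96% | 87% |

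The MAR power of 88% exceeds the planned 80.5% because the always-observed interim value recovers information. That is a feature of the set-up, not a prediction for the trial.

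**4. Carrying this to percentage change.** Dividing by baseline BMI scales the MAR and MNAR results by about the same factor, so the relative gap carries over. The protocol gives no expected baseline BMI, so the illustration stays in kg/m².

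**The case against.** The strongest reply has four parts.

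- **MMRM is only a default.** The sentence opens with "Unless specified, for all other secondary efficacy endpoints", and imputation details go to the SAP, which is not at hand and could align the two analyses. This is true. But the protocol does state a method for this endpoint and nowhere exempts it, so this is a choice already on paper and not a detail left open.
- **Dropout is not the same as missing BMI.** Sections 9.1 and 9.5.5 plan to follow subjects who stop treatment, Section 9.3.3 asks investigators to bring early discontinuers in for the primary endpoint, and home visits are available. Missing Week 52 BMI may be well below 40%, which narrows any gap. This stands, and is why 10% and 20% are shown.
- **MMRM need not be an on-drug analysis.** Section 9.7.1.6 uses the Full Analysis Set for all efficacy analyses, and Section 9.7.1.2 defines that set irrespective of adherence. Nothing keeps off-drug values out of the MMRM, so it cannot be said to extrapolate on-drug trajectories. This stands. The remaining difference concerns values that were never collected.
- **An MAR-based secondary beside an MNAR primary is defensible.** For another measurement, such as waist circumference, it would be. Here the values are the same, and the protocol follows the consistent route for the Z-score.

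A reader might go further and infer that the two results will disagree, that the secondary will be the more favourable, or that it overstates the effect by 1/0.6 = 1.67-fold. The documents do not support this. They name no reference-based mechanism, and MNAR alone fixes no direction. The 1.67 arises only from assuming jump-to-placebo with 40% missing in both arms; other assumptions give no gap or the reverse order.

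**Conclusion.** The inconsistency is real and lies in the current Section 9.7.1.6: two missing-data assumptions for one measurement, without a reason. That the MMRM relies on MAR is inferred from the method; the sentence itself does not say so.

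The consequence is that relative effects and p-values for absolute and percentage change may differ for reasons other than scale. In the equal-missingness cases examined, the gap runs from nil to 40% of a 1 kg/m² effect, and unequal missingness can reverse its sign. These figures rest on assumed mechanisms, an assumed MAR effect of 1 kg/m² and, for power, the simplified simulation. They show what is possible and are not forecasts.

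The primary test, its power and its type I error are untouched, since percentage change stands outside the controlled sequence. A report could also explain the discrepancy by stating both assumptions. This is a cheap improvement to the coherence of a secondary endpoint, not a threat to the trial's main conclusion.

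**What to change.** In Section 9.7.1.6, and in the matching synopsis text, take percentage change in BMI out of the MMRM default. Suggested wording:

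*Percentage change in BMI from Baseline to Week 52 will be derived within each of the primary analysis's imputed BMI datasets, analysed by the same ANCOVA (treatment, sex, baseline age, baseline BMI) and combined by Rubin's rules. An MMRM will be reported as a sensitivity analysis under MAR.*

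This treats percentage change as the Z-score is already treated. It needs no new data and no new imputation, only one extra model on datasets that will exist anyway. The downside is that the reported percentage effect may be smaller than the MMRM would give, depending on the mechanism that the SAP fixes. The change should be made before unblinding.

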9.7.1.7 Pharmacokinetic, Pharmacodynamic, Pharmacogenomic, and Other Biomarker Analyses

9.7.1.7.1 PHARMACOKINETIC ANALYSES

Lorcaserin plasma concentration-time data will be subjected to population PK analysis using nonlinear mixed effects modeling. The effect of covariates, such as baseline characteristics or demographics, on PK will be explored. Derived exposure parameters such as the maximum observed concentration and the area under the concentration-time curve from time 0 to 24 hours at steady-state will be calculated from the final PK model using individual posterior estimates of the PK parameters and from dosing history. The PK analysis set will be used for this analysis.

9.7.1.7.2 PHARMACODYNAMIC ANALYSES

Change from Baseline in BMI will be assessed as the PD endpoint. The PD analysis set will be used for this analysis.

Other assessments (eg, percentage of BMI change, proportion [%] of patients achieving $\geq 5\%$ and $\geq 10\%$ BMI reduction, and change in waist circumference from baseline) will also be assessed as part of the PD analysis. The PK/PD analysis set will be used for this analysis.

9.7.1.7.3 PHARMACOKINETIC/PHARMACODYNAMIC ANALYSES

Population PK/PD modeling will be used to explore the relationship between lorcaserin plasma exposure and response, including but not limited to change in BMI from baseline and the probability of achieving at least a 5% and at least a 10% change in BMI from baseline to Week 52. Additionally, exposure-safety relationships for select safety parameters may be explored graphically, depending on the data at the end of study. Any emergent relationship may be modeled as appropriate. Any parameters based on the study data may be considered for exploratory assessment for its relationship to PK.

9.7.1.7.4 PHARMACOGENOMIC AND PHARMACOGENETIC ANALYSES

Not applicable

9.7.1.8 Safety Analyses

Evaluations of safety will be performed on the Safety Analysis Set. Safety assessments including the incidence of AEs (including changes from baseline in physical examination, neuromuscular sign assessment, and signs and symptoms of priapism and hyperprolactinemia), out-of-normal-range laboratory safety test values, change from baseline in laboratory safety test values, ECGs, and vital sign measurements will be summarized by treatment group using descriptive statistics or frequency count as appropriate. (revised per Amendment 01)

No hypothesis testing will be performed for the safety assessment.

Study Day 1 for all safety analyses will be defined as the date of the 1st dose of study drug.

9.7.1.8.1 EXTENT OF EXPOSURE

Subjects will receive Belviq XR 20 mg or placebo QD for up to 52 weeks. The extent of exposure will be characterized by duration of exposure (in weeks) for each treatment group.

Duration of exposure will be defined as the number of weeks between the date the subject received the 1st dose of study drug and the date the subject received the last dose of study drug. Duration of exposure will be summarized using descriptive statistics by treatment group. In addition, the duration of exposure will be categorized and will be summarized using frequency count by treatment group.

9.7.1.8.2 ADVERSE EVENTS

The AE verbatim descriptions (investigator terms from the CRF) will be classified into standardized medical terminology using the Medical Dictionary for Regulatory Activities (MedDRA). Adverse events will be coded to the MedDRA (Version 18.0 or higher) lower level term closest to the verbatim term. The linked MedDRA PT and primary system organ class (SOC) are also captured in the database.

A treatment-emergent AE (TEAE) is defined as an AE that emerges during treatment (up to 28 days after the last dose of study drug), having been absent at pretreatment (Baseline) or

- Reemerges during treatment (up to 28 days after the last dose of study drug), having been present at pretreatment (Baseline) but stopped before treatment, or
- Worsens in severity during treatment relative to the pretreatment state, when the AE is continuous.

Only those AEs that were treatment emergent will be included in summary tables. All AEs, treatment emergent or otherwise, will be presented in subject data listings.

The TEAEs will be summarized by treatment group. The following summaries will be reported for TEAEs:

- Incidence of TEAEs in descending order of frequency
- Incidence of TEAEs by SOC and PT
- Incidence of treatment-related TEAEs by SOC and PT
- Incidence of TEAEs by SOC, PT and maximum severity (mild, moderate, or severe)
- Incidence of treatment-related TEAEs by SOC, PT, and maximum severity (mild, moderate, or severe)
- Incidence of TEAEs by SOC, PT, and relationship to study drug (Yes [related] or No [not related])

A subject will be counted only once within a SOC or PT, if the subject experienced more than 1 TEAE within a specified SOC and PT.

The following summaries will also be presented for the treatment-emergent SAEs.

- Incidence of TEAEs leading to death
- Incidence of treatment-emergent SAE by SOC and PT
- Incidence of treatment-related treatment-emergent SAE by SOC and PT

In addition, subjects with TEAEs leading to discontinuation from study drug and AEs of special interest as described in [Section 9.5.4.3.2](#) will be summarized by MedDRA SOC and PT for each treatment group.

